4.2 Endpoints

4.2.1 Effectiveness

Primary:

- % EWL at 12 months from randomization by randomized arm measured at the week 52 visit. The null hypothesis is no difference in mean %EWL between randomized arms.

Secondary:

- Proportion with $\geq 25\%$ EWL at 12 months by randomized arm
- Change in hypertension in the ESG group compared to LS only

- Proportion of patients off or with reduction in their antihypertensive medications in the randomized control arm compared to lifestyle control at 12 months
- Change in systolic and diastolic blood pressure in the randomized arm compared to lifestyle control at 12 months
- Comparing diastolic and systolic blood pressures as continuous variables 12 months after ESG (compared to baseline) in the entire cohort that received ESG both in the randomized and cross-over segments of the trial
- Change in type II diabetes in the ESG groups compared to LS only
 - Proportion of patients off or with reduction in their diabetes medications in the randomized arm compared to lifestyle control at 12 months
 - Change in HgbA1c in the randomized arm compared to lifestyle control at 12 months
 - Comparing HgbA1c as a continues variable 12 months after ESG (compared to before) in the entire cohort that received ESG both in the randomized and cross-over segments of the trial.
- %TBWL in the ESG group compared to LS only
- % of patients in the ESG group achieving > 5% TBWL compared to LS only
- % of patients in the ESG group achieving > 10% TBWL compared to LS only
- Durability of the plication evaluated by endoscopy at 12 months (level 1) and effectiveness of re-tightening procedure performed at 12 months (level 1) in maintaining and / or enhancing weight loss at 24 months. Durability of the plication and procedure is defined as greater than 70% of the cohort undergoing repeat endoscopy achieving a score of ≥ 1 out of 3 prior to re-tightening (Grading system and evaluation in appendix). Efficacy of re-tightening is defined as $\geq 50\%$ of the cohort undergoing the re-tightening maintaining or losing weight compared to the re-tightening weight at 12 months after the re-tightening procedure.
- Incidence of esophagitis at repeat endoscopy at 12 months (level 1). (LA grading system in form in appendix)
- Changes in quality of life assessed using standard validated questionnaires (IWQOL-lite and SF-36)
- Changes in depression assessed using PHQ-9 questionnaire

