5.5 Trial Intervention

5.5.1.1.1 Control group

Participants randomized to the control group (lifestyle intervention only) in Level 1 will undergo a standard moderate intensity life-style intervention during the first 12 months of Level 1. The first dietary visit will be scheduled on the day of randomization. A low-calorie diet plan will be reviewed with each participant and will be adjusted according to each participant's needs. Participants in the control group will not undergo the liquid transitional diet as it is difficult to achieve compliance without intervention. Physical activity, including 150 minutes of aerobic exercise per week, will be encouraged and assessed for compliance during the study. Participants will have 12 follow-up visits in the 12 months of Level 1 as described in the schedule of events. Participants will receive \$100 for every 4 visits they attend consecutively in Level 1 with the ability to earn a maximum of \$300 at the end of the first 12 months of Level 1.

Control group participants who were compliant with at least 75% of visits in the first 12 months of Level 1, have not achieved $\geq 25\%$ EWL measured at the week 52 visit, or still have a BMI ≥ 30 and ≤ 40 , and have no new psychosocial contraindications as deemed by the treatment team to the procedure will cross over to receive ESG in Level 2, in addition to the standard moderate intensity lifestyle intervention program for 12 months. After crossing over into Level 2, participants will be able to earn the same remuneration as in Level 1 (\$100 for every 4 consecutive visits attended). Those who were compliant with attending 75% of the visits in Level 2 (second 12 months) will receive a bonus of \$300 at the final study visit, for a potential total of \$900 earned in the two years.

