ESG patients will undergo a standard moderate intensity life-style intervention administered over 12 visits in the first year after ESG. Participants will be required to follow up with their prescribing physician to make any necessary changes to their hypertension and/or type II diabetes medications at 3, 6, 9 and 12 months. Completion of patient follow-up with providers for medication adjustment will be captured with completion of the appropriate CRF at the corresponding visits. In the event that participants are unable to contact their physician or participants are experiencing symptoms related to the medication dosing requiring urgent action, the study team will make any necessary

changes in their medication dosing and document these changes appropriately in the relevant CRFs. Any medication changes will be monitored and recorded by the study team.

All ESG patients in Level 1 (80) will be evaluated for %EWL at the end of Level 1 (measurement of primary endpoint). Those ESG patients who have achieved >25% EWL at the end of Level 1 will not undergo a repeat endoscopy and will continue to follow-up with a lifestyle intervention in Level 2. Those ESG patients who have not achieved >25% EWL at the end of Level 1 will undergo a repeat upper endoscopy at 52 to 60 weeks to assess the durability of the plications (see Plication Durability form), and perform a retightening of the ESG if needed. The need for re-tightening will be determined by the PI after evaluating the sutures based on a grading system presented in the retightening CRF. The retightening procedure will be performed if at least one of the three portions (proximal, mid, and distal) of the endoscopic sleeve is non-tubular in shape. For each tubular third of the sleeve, 1 point will be given. A score of 3/3 means the entire (proximal, mid, and distal) sleeve is tubular in shape. A score of 2/3 means that one-third of the sleeve is no longer tubular. A score of 1/3 means that two-thirds of the sleeve are no longer tubular. Finally a score of 0/3 means the entire sleeve is no longer tubular. Re-tightening will occur for patients with a score of 0, 1 or 2.

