5.6 Schedule of Events

5.6.1.1 Schedule of Events for Treatment Group, Year 1, Level 1

TABLE 1. MERIT SCHEDULE OF EVENTS (Year 1, Level 1, Treatment Group, 80 patients)											
	Enrollment; Screening/ Baseline	Randomization	ESG Procedure	Post-Op Phone Call	Weeks 1, 4, 8	Week 12	Weeks 16, 20	Week 24 (6 month)	Weeks 30, 36, 42, 48	Week 52 (Final Year 1 visit)	Unscheduled Visit
Visit Number	-1		0	-	1,2,3	4	5,6	7	8,9,10,11	12	
Informed consent	X										
Complete Physical Exam (CPE) by Investigator or Investigator delegated / medically qualified team member	X					X		X	X	X	X
Investigator or Investigator delegated/medically qualified team member exam					X	X	X	X	X	X	X
EKG if (> 50 yo)	X										
Formal nutritional assessment	X										
Formal psychology evaluation	X										
Pregnancy test (females of childbearing potential only)	X										
Laboratory tests, H-pylori breath testing (baseline only)**	X							X		X	
Questionnaires#	X					X		X		X	
Inclusion/exclusion criteria	X										
Endoscopy / Procedure			X								
Procedure Assessment Form			X								
GERD Questionnaire + Activity Assessment Form	X				X	X	X	X	X	X	
Weight, BMI/height, Waist and Hip Circumference Form	X		X		X	X	X	X	X	X	X
Vital Signs Form	X		X		X	X	X	X	X	X	X
Adverse Events Form			X	X	X	X	X	X	X	X	X
Medications Form##	X		X	X	X	X	X	X	X	X	X
Post-enrollment Nutrition / Exercise / satiety counseling and assessment		X++			X	X	X	X	X	X	
Randomization to ESG+	X	X									
Subject Satisfaction Questionnaire (treatment phase)										X	

** Electrolytes, Creatinine, CBC, Iron, TIBC, B12, 25-hydroxy Vitamin D, TSH, HgA1c, fasting blood sugar and insulin, PTT, fasting lipids profile (total cholesterol, LDL, HDL, and Triglyceride), ALT, AST, ALK-P, total bilirubin, direct bilirubin, BUN, total protein, albumin, CRP, urinalysis; also include PY-Y-1, GLP-1 and total Ghrelin pending sites' availability to analyze

Eating disorder questionnaire + hospital anxiety and depression questionnaires (only at base-line), IWFQOL-Lite, SF36, PHQ9, Pittsburgh Sleep Quality Index (PSQI), Three factor eating questionnaire (TFEQ)

Record all medications including dose and frequency; especially diabetes and blood pressure medication.

+ To occur after all screening assessments are complete; within 45 days of screening evaluations

++ Nutritional visit to discuss upcoming post-op liquid diet

5.6.1.1.2 Schedule of Events for Treatment Group, Year 2, Level 2

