	Enrollment; Screening/ Baseline	Randomization / Week 1 visit	Weeks 4, 8	Week 12	Weeks 16, 20	Week 24 (6 month)	Weeks 30, 36, 42, 48	Week 52 (Final Year 1 visit), re-screen for crossover to ESG	Unscheduled Visit
Visit Number	-1	1	2,3	4	5,6	7	8,9,10,11,	12	
Informed consent	X								
Complete Physical Exam (CPE) by Investigator or Investigator delegated / medically qualified team member	X			X		X	X	X	X
Investigator or Investigator delegated/medically qualified team member exam		X ⁺⁺	X	X	X	X	X	X	X
EKG if (> 50 yo)	X							X	
Formal nutritional assessment	X								
Formal psychology evaluation	X								
Pregnancy test (females of childbearing potential only)	X								
Laboratory tests, H-pylori breath testing (baseline only)* *	X							X	
Questionnaires#	X			X		X		X	
Inclusion/exclusion criteria	X							X	
Endoscopy / Procedure									
Procedure Assessment Form									
GERD Questionnaire + Activity Assessment Form	X	X	X	X	X	X	X	X	
Weight, BMI/height, Waist and Hip Circumference Form	X	X	X	X	X	X	X	X	X
Vital Signs Form	X	X	X	X	X	X	X	X	X
Adverse Events Form		X	X	X	X	X	X	X	X
Medications Form##	X	X	X	X	X	X	X	X	X
Post-enrollment Nutrition / Exercise / satiety counseling and assessment		X	X	X	X	X	X	X	
Randomization to ESG vs. LS ⁺		X							
Subject Satisfaction Questionnaire (control phase)								X	

** Electrolytes, Creatinine, CBC, Iron, TIBC, B12, 25-hydroxy Vitamin D, TSH, HgA1c, fasting blood sugar and insulin, PTT, fasting lipids profile (total cholesterol, LDL, HDL, and Triglyceride), ALT, AST, ALK-P, total bilirubin, direct bilirubin, BUN, total protein, albumin, CRP, urinalysis; also include PYY-1, GLP-1 and total Ghrelin pending sites' availability to analyze

Eating disorder questionnaire + hospital anxiety and depression questionnaires (only at base-line), IWFQOL-Lite, SF36, PHQ9, Pittsburgh Sleep Quality Index (PSQI), Three factor eating questionnaire (TFEQ)

Record all medications including dose and frequency; especially diabetes and blood pressure medication.

+ LS start with the week 1 visit with no transitional diet.

++ Required only for Week 1 visit

5.6.1.1.4 Schedule of Events for Control Group, Crossover in Year 2, Level 2

[figure not shown]
TABLE 3. MERIT SCHEDULE OF EVENTS (Year 2, Level 2, Control Group, cross-over 120 patients)									
	ESG Procedure	Post-Op Phone Call	Weeks 1, 4, 8	Week 12	Weeks 16, 20	Week 24 (6 month)	Weeks 30, 36, 42, 48	Week 52 (Final Year 1 visit)	Unscheduled Visit
Visit Number	0	-	1,2,3	4	5,6	7	8,9,10,11	12	

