Informed consent for cross-over procedure									
Complete Physical Exam (CPE) by Investigator or Investigator delegated / medically qualified team member				X		X	X	X	X
Investigator or Investigator delegated/medically qualified team member exam			X	X	X	X	X	X	X
EKG if (> 50 yo)									
Pregnancy test (females of childbearing potential only)									
Laboratory tests **						X		X	
Questionnaires#				X		X		X	
Endoscopy / Procedure	X								
Procedure Assessment Form	X								
GERD Questionnaire+ Activity Assessment Form			X	X	X	X	X	X	
Weight, BMI/height, Waist and Hip Circumference Form	X		X	X	X	X	X	X	X
Vital Signs Form	X		X	X	X	X	X	X	X
Adverse Events Form	X	X	X	X	X	X	X	X	X
Medications Form##	X	X	X	X	X	X	X	X	X
Post-enrollment Nutrition / Exercise/ satiety counseling and assessment			X	X	X	X	X	X	
Subject Satisfaction Questionnaire (treatment phase)								X	

** Electrolytes, Creatinine, CBC, Iron, TIBC, B12, 25-hydroxy Vitamin D, TSH, HgA1c, fasting blood sugar and insulin, PTT, fasting lipids profile (total cholesterol, LDL, HDL, and Triglyceride), ALT, AST, ALK-P, total bilirubin, direct bilirubin, BUN, total protein, albumin, CRP, urinalysis; also include PYY-1, GLP-1 and total Ghrelin pending sites' availability to analyze

Eating disorder questionnaire+ hospital anxiety and depression questionnaires (only at baseline), IWFQOL-Lite, SF36, PHQ9, Pittsburgh Sleep Quality Index (PSQI), Three factor eating questionnaire (TFEQ)

Record all medications including dose and frequency; especially diabetes and blood pressure medication.

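### As written, prescriber review of hypertension and diabetes drugs is required only in the Treatment Group section, so the two 12-month medication-reduction endpoints may partly reflect unequal prompting

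*Combined protocol and SAP*

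**What the plan says.** Section 4.2.1 lists two between-arm secondary endpoints that depend on prescribing. For diabetes: "Proportion of patients off or with reduction in their diabetes medications in the randomized arm compared to lifestyle control at 12 months". For hypertension: "Proportion of patients off or with reduction in their antihypertensive medications in the randomized control arm compared to lifestyle control at 12 months". The second names a control arm on both sides; I read the first mention as the ESG arm, in line with its parent bullet. Section 4.1 describes the trial as open-label.

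Section 5.5.1.1.2, in a paragraph that opens with ESG patients and the first year after the procedure, says: "Participants will be required to follow up with their prescribing physician to make any necessary changes to their hypertension and/or type II diabetes medications". The times given are 3, 6, 9 and 12 months. It continues: "Completion of patient follow-up with providers for medication adjustment will be captured with completion of the appropriate CRF at the corresponding visits". The study team may change doses itself if the physician cannot be reached or symptoms are urgent. Earlier in the section, participants on these drugs are told to inform their prescriber of the procedure and discuss changes for the period after it.

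Section 5.5.1.1.1 covers diet, activity, visits, payment and crossover for controls. On follow-up it says: "Participants will have 12 follow-up visits in the 12 months of Level 1 as described in the schedule of events". It does not mention review of hypertension or diabetes drugs.

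**The concern.** Whether a drug is stopped or reduced is a prescriber's decision, not a measurement. Its frequency depends on the patient's condition and also on how often someone is asked to decide. Here the prompt comes after randomization and, as written, in one arm only, so randomization does not balance it. The prescriber can know the arm, and the plan states no common titration rule. Section 7.2.2 assigns binary outcomes to a Pearson chi-square test, which cannot separate a benefit of weight loss from the effect of extra review.

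At stake is the medication part of Objective 2, the effect of ESG on hypertension and diabetes. A difference in these two proportions could be reported as an effect of ESG when part of it comes from closer medication follow-up.

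**Working it through.** The plan gives no power figure or expected proportion for these endpoints (section 7.1 concerns %EWL), so there is no stated number to reproduce. The check sets the two arms' text and schedules side by side for year 1.

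| Item, year 1 | ESG arm | Control arm |
|---|---|---|
| Required prescriber review (5.5.1.1.2; 5.5.1.1.1) | 3, 6, 9, 12 months = 4 | none stated |
| CRF confirming the review took place | yes | none stated |
| Study-team dose changes as back-up | yes | none stated |
| Instruction to discuss drugs with prescriber before the procedure | yes | none stated |
| Laboratory panel (5.6, Level 1 tables) | baseline, Week 24, Week 52 = 3 | baseline, Week 52 = 2 |
| Investigator or delegate exam | 12 visits | 12 visits |
| Medications Form | every clinic visit | every clinic visit |

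1. *Prescriber review.* Neither arm's schedule has a row for it, so the schedules neither supply it for controls nor rule it out. The only statement is in the Treatment Group text.

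2. *Laboratory panel.* The row "Laboratory tests, H-pylori breath testing (baseline only" appears in both Level 1 tables. The footnoted panel includes HbA1c: "Electrolytes, Creatinine, CBC, Iron, TIBC, B12, 25-hydroxy Vitamin D, TSH, HgA1c, fasting blood sugar and insulin, PTT, fasting lipids profile". Between baseline and Week 52 the ESG arm has 3 − 2 = 1 HbA1c and the control arm 2 − 2 = 0. In the Level 2 control table the panel is marked at Week 24 and Week 52 after crossover ESG, so the interim panel goes with having had ESG.

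3. *What is equal.* The row "Investigator or Investigator delegated/medically qualified team member exam" is marked in both arms at weeks 1, 4, 8, 12, 16, 20, 24, 30, 36, 42, 48 and 52, that is 12 visits each. Drug use is therefore recorded about equally, and a medically qualified person sees both arms equally often. That equalises ascertainment of the endpoint. It does not equalise a required visit to the prescriber.

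4. *Who is affected.* Section 4.5 allows at most 50 of 200 participants without comorbidity, so at least 200 − 50 = 150 have hypertension or diabetes. At 2:3 allocation that is about 150 × 2/5 = 60 ESG and 150 × 3/5 = 90 control participants. A comorbidity that only meets its quota of 50 gives about 20 against 30 for its endpoint.

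5. *Direction.* The required contact is for any change that is needed, which includes increases. More review could raise or lower the proportion reduced.

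**The case against.** The strongest reply is that both arms may have been meant. The paragraph moves from ESG patients to the general word 'Participants', and the medication-review CRF is not in the text supplied. The contrast is therefore a requirement against silence, not four against a stated zero, and nothing bars controls from seeing their prescribers in usual care. This stands, and it is why the conclusion is limited to the text as written. It does not remove the need for a change: a site reading the Control group section would not learn that the review applies there.

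A second reply is that closer review belongs to ESG care, given general anaesthesia and four weeks of liquid diet. That is a good reason to keep the review. But section 4.1 frames the comparison as ESG added to lifestyle intervention against lifestyle intervention alone. If the review is part of the treatment strategy, the two endpoints should be labelled that way.

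A third is that Objective 2 does not rest on drug counts alone. Between-arm changes in blood pressure and HbA1c at 12 months are already secondary endpoints, analysed by ANCOVA. This also stands and limits the consequence.

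A reader might infer from the unequal Week 24 panel that the protocol contradicts its own statement that the ESG arm follows the control visit schedule. It does not. That statement opens a paragraph on visits and payments, the visit weeks match, and laboratory tests are dealt with separately. The panel difference counts only as a second contrast in monitoring.

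**Conclusion.** The point holds as a matter of design and wording. If the text is followed, the ESG arm has four required prescriber reviews, a pre-procedure prompt and one interim HbA1c, while none of these is stated for controls. Part of any between-arm difference in the two medication-reduction proportions could then come from unequal prompting. This assumes that sites apply the Treatment Group paragraph to that arm only.

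A reader might go further and infer that the endpoints are biased in favour of ESG, or that their false-positive rate is inflated by some amount. The documents support neither. They give no rate of drug reduction, no rate at which reviews lead to changes and no usual-care contact rate for controls, so size and sign remain unknown. Any numerical illustration would simply return the gap assumed for it. Nor do the documents say that controls will go without review.

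The primary %EWL endpoint is not affected. Two secondary endpoints are, and the change is worth making because it is cheap.

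**What to change.** State in 5.5.1.1.1 that control participants on hypertension or diabetes drugs have the same prescriber review, CRF and study-team back-up as the ESG arm, at the existing week 12, 24, 36 and 52 visits. If this was always intended, the sentence settles it. Keep the ESG-arm review.

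In reporting, show medication change by arm as reduced, unchanged or increased, beside the blood pressure and HbA1c results already planned, so that a lower dose can be read together with the level of control. An added Week 24 HbA1c for controls with diabetes would close the second contrast but is optional.

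If the review stays in one arm, keep the planned test, describe the comparison for these two endpoints as ESG plus required medication review against lifestyle intervention, and state the unequal review as a limitation.

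The cost is one protocol sentence, an existing CRF at existing visits, and a table from data already collected. The burden is four prescriber contacts per affected control. With about 90 such controls (the minimum implied by the quota) and full attendance, that is 90 × 4 = 360 contacts, some of which may happen in usual care anyway. The optional HbA1c adds one blood draw per control with diabetes. Open-label prescriber discretion remains even with equal review.

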5.6 Schedule of Events

5.6.1.1 Schedule of Events for Treatment Group, Year 1, Level 1

TABLE 1. MERIT SCHEDULE OF EVENTS (Year 1, Level 1, Treatment Group, 80 patients)											
	Enrollment; Screening/ Baseline	Randomization	ESG Procedure	Post-Op Phone Call	Weeks 1, 4, 8	Week 12	Weeks 16, 20	Week 24 (6 month)	Weeks 30, 36, 42, 48	Week 52 (Final Year 1 visit)	Unscheduled Visit
Visit Number	-1		0	-	1,2,3	4	5,6	7	8,9,10,11	12	
Informed consent	X										
Complete Physical Exam (CPE) by Investigator or Investigator delegated / medically qualified team member	X					X		X	X	X	X
Investigator or Investigator delegated/medically qualified team member exam					X	X	X	X	X	X	X
EKG if (> 50 yo)	X										
Formal nutritional assessment	X										
Formal psychology evaluation	X										
Pregnancy test (females of childbearing potential only)	X										
Laboratory tests, H-pylori breath testing (baseline only)**	X							X		X	
Questionnaires#	X					X		X		X	
Inclusion/exclusion criteria	X										
Endoscopy / Procedure			X								
Procedure Assessment Form			X								
GERD Questionnaire + Activity Assessment Form	X				X	X	X	X	X	X	
Weight, BMI/height, Waist and Hip Circumference Form	X		X		X	X	X	X	X	X	X
Vital Signs Form	X		X		X	X	X	X	X	X	X
Adverse Events Form			X	X	X	X	X	X	X	X	X
Medications Form##	X		X	X	X	X	X	X	X	X	X
Post-enrollment Nutrition / Exercise / satiety counseling and assessment		X++			X	X	X	X	X	X	
Randomization to ESG+	X	X									
Subject Satisfaction Questionnaire (treatment phase)										X	

** Electrolytes, Creatinine, CBC, Iron, TIBC, B12, 25-hydroxy Vitamin D, TSH, HgA1c, fasting blood sugar and insulin, PTT, fasting lipids profile (total cholesterol, LDL, HDL, and Triglyceride), ALT, AST, ALK-P, total bilirubin, direct bilirubin, BUN, total protein, albumin, CRP, urinalysis; also include PY-Y-1, GLP-1 and total Ghrelin pending sites' availability to analyze

Eating disorder questionnaire + hospital anxiety and depression questionnaires (only at base-line), IWFQOL-Lite, SF36, PHQ9, Pittsburgh Sleep Quality Index (PSQI), Three factor eating questionnaire (TFEQ)

Record all medications including dose and frequency; especially diabetes and blood pressure medication.

+ To occur after all screening assessments are complete; within 45 days of screening evaluations

++ Nutritional visit to discuss upcoming post-op liquid diet

5.6.1.1.2 Schedule of Events for Treatment Group, Year 2, Level 2

TABLE 2. MERIT SCHEDULE OF EVENTS (Year 2, Level 2, Treatment Group, 80 Patients)							
	ESG retightening [†]	Post-Op Clinical Eval ^{**}	Follow-up after ESG retightening OR Week 60 [†]	Week 72-76*	Weeks 80, 88, 96	Week 104 (Final Year 2 visit)	Unscheduled Visit
Visit Number	17	-	18	19	20, 21, 22	23	
Informed consent							
Complete Physical Exam (CPE) by Investigator or Investigator delegated / medically qualified team member				X		X	X
Investigator or Investigator delegated/medically qualified team member exam			X	X	X	X	X
EKG if (> 50 yo)							
Formal nutritional assessment							
Formal psychology evaluation							
Pregnancy test (females of childbearing potential only)							
Laboratory tests ^{**}				X		X	
Questionnaires [#]				X		X	
Inclusion/exclusion criteria							
Endoscopy / Procedure	X						
Procedure Assessment Form	X						
GERD Questionnaire + Activity Assessment Form			X	X	X	X	
Weight, BMI/height, Waist and Hip Circumference Form	X		X	X	X	X	X
Vital Signs Form	X		X	X	X	X	X
Adverse Events Form		X	X	X	X	X	X
Medications Form ^{##}			X	X	X	X	X
Post-enrollment Nutrition / Exercise / satiety counseling and assessment			X	X	X	X	
Subject Satisfaction Questionnaire (study termination)						X	

** Electrolytes, Creatinine, CBC, Iron, TIBC, B12, 25-hydroxy Vitamin D, TSH, HgA1c, fasting blood sugar and insulin, PTT, fasting lipids profile (total cholesterol, LDL, HDL, and Triglyceride), ALT, AST, ALK-P, total bilirubin, direct bilirubin, BUN, total protein, albumin, CRP, urinalysis; also include PYY-1, GLP-1 and total Ghrelin pending sites' availability to analyze

IWFQOL-Lite, SF36, PHQ9, Pittsburg Sleep Quality Index (PSQI), Three factor eating questionnaire (TFEQ)

Record all medications including dose and frequency; especially diabetes and blood pressure medication.

++ Post-op phone call, no clinic visit, to occur between 18-36 hours post-op

+ ESG retightening to occur between Weeks 52-60 for those who qualify with in-clinic follow-up visit to occur 4 weeks post retightening, or subjects to continue to Week 60 for those who do not qualify for ESG retightening

*Lab draw to occur between Week 72-76

5.6.1.1.3 Schedule of Events for Control Group, Crossover in Year 1, Level 1

TABLE 3. MERIT SCHEDULE OF EVENTS (Year 1, Level 1, Control Group, 120 patients)									
	Enrollment; Screening/ Baseline	Randomization / Week 1 visit	Weeks 4, 8	Week 12	Weeks 16, 20	Week 24 (6 month)	Weeks 30, 36, 42, 48	Week 52 (Final Year 1 visit), re-screen for crossover to ESG	Unscheduled Visit
Visit Number	-1	1	2,3	4	5,6	7	8,9,10,11,	12	
Informed consent	X								
Complete Physical Exam (CPE) by Investigator or Investigator delegated / medically qualified team member	X			X		X	X	X	X
Investigator or Investigator delegated/medically qualified team member exam		X ⁺⁺	X	X	X	X	X	X	X
EKG if (> 50 yo)	X							X	
Formal nutritional assessment	X								
Formal psychology evaluation	X								
Pregnancy test (females of childbearing potential only)	X								
Laboratory tests, H-pylori breath testing (baseline only)* *	X							X	
Questionnaires#	X			X		X		X	
Inclusion/exclusion criteria	X							X	
Endoscopy / Procedure									
Procedure Assessment Form									
GERD Questionnaire + Activity Assessment Form	X	X	X	X	X	X	X	X	
Weight, BMI/height, Waist and Hip Circumference Form	X	X	X	X	X	X	X	X	X
Vital Signs Form	X	X	X	X	X	X	X	X	X
Adverse Events Form		X	X	X	X	X	X	X	X
Medications Form##	X	X	X	X	X	X	X	X	X
Post-enrollment Nutrition / Exercise / satiety counseling and assessment		X	X	X	X	X	X	X	
Randomization to ESG vs. LS ⁺		X							
Subject Satisfaction Questionnaire (control phase)								X	

** Electrolytes, Creatinine, CBC, Iron, TIBC, B12, 25-hydroxy Vitamin D, TSH, HgA1c, fasting blood sugar and insulin, PTT, fasting lipids profile (total cholesterol, LDL, HDL, and Triglyceride), ALT, AST, ALK-P, total bilirubin, direct bilirubin, BUN, total protein, albumin, CRP, urinalysis; also include PYY-1, GLP-1 and total Ghrelin pending sites' availability to analyze

Eating disorder questionnaire + hospital anxiety and depression questionnaires (only at base-line), IWFQOL-Lite, SF36, PHQ9, Pittsburgh Sleep Quality Index (PSQI), Three factor eating questionnaire (TFEQ)

Record all medications including dose and frequency; especially diabetes and blood pressure medication.

+ LS start with the week 1 visit with no transitional diet.

++ Required only for Week 1 visit

5.6.1.1.4 Schedule of Events for Control Group, Crossover in Year 2, Level 2

[figure not shown]
TABLE 3. MERIT SCHEDULE OF EVENTS (Year 2, Level 2, Control Group, cross-over 120 patients)									
	ESG Procedure	Post-Op Phone Call	Weeks 1, 4, 8	Week 12	Weeks 16, 20	Week 24 (6 month)	Weeks 30, 36, 42, 48	Week 52 (Final Year 1 visit)	Unscheduled Visit
Visit Number	0	-	1,2,3	4	5,6	7	8,9,10,11	12	
Informed consent for cross-over procedure									
Complete Physical Exam (CPE) by Investigator or Investigator delegated / medically qualified team member				X		X	X	X	X
Investigator or Investigator delegated/medically qualified team member exam			X	X	X	X	X	X	X
EKG if (> 50 yo)									
Pregnancy test (females of childbearing potential only)									
Laboratory tests **						X		X	
Questionnaires#				X		X		X	
Endoscopy / Procedure	X								
Procedure Assessment Form	X								
GERD Questionnaire+ Activity Assessment Form			X	X	X	X	X	X	
Weight, BMI/height, Waist and Hip Circumference Form	X		X	X	X	X	X	X	X
Vital Signs Form	X		X	X	X	X	X	X	X
Adverse Events Form	X	X	X	X	X	X	X	X	X
Medications Form##	X	X	X	X	X	X	X	X	X
Post-enrollment Nutrition / Exercise/ satiety counseling and assessment			X	X	X	X	X	X	
Subject Satisfaction Questionnaire (treatment phase)								X	

** Electrolytes, Creatinine, CBC, Iron, TIBC, B12, 25-hydroxy Vitamin D, TSH, HgA1c, fasting blood sugar and insulin, PTT, fasting lipids profile (total cholesterol, LDL, HDL, and Triglyceride), ALT, AST, ALK-P, total bilirubin, direct bilirubin, BUN, total protein, albumin, CRP, urinalysis; also include PYY-1, GLP-1 and total Ghrelin pending sites' availability to analyze

Eating disorder questionnaire+ hospital anxiety and depression questionnaires (only at baseline), IWFQOL-Lite, SF36, PHQ9, Pittsburgh Sleep Quality Index (PSQI), Three factor eating questionnaire (TFEQ)

Record all medications including dose and frequency; especially diabetes and blood pressure medication.

